data_SAR	Yes	imp_ana_lv_pns_amp_01_04 ³⁶	Phrenic nerve stimulation threshold [V] at 0.4 ms	scale	n.a.
data_SAR	Yes	imp_ana_lv_pns_amp_01_05 ³⁷	Phrenic nerve stimulation threshold [V] at 0.5 ms	scale	n.a.

Pacing threshold measurements will be reported for 0.4 and 0.5 ms separately. See the justification above.

The above analyses are performed for the following 12 vector permutations, respectively:

- 01 LV1 tip to LV2 ring
- 02 LV1 tip to LV4 ring
- 03 LV1 tip to RV coil
- 04 LV1 tip to ICD
- 05 LV2 ring to LV1 tip
- 06 LV2 ring to LV4 ring
- 07 LV2 ring to RV coil
- 08 LV3 ring to LV2 ring
- 09 LV3 ring to LV4 ring
- 10 LV3 ring to RV coil
- 11 LV4 ring to LV2 ring
- 12 LV4 ring to RV coil

³⁴ IF imp_ana_lv_pulse_01 =0.4 THEN imp_ana_lv_thresh_01_04 = imp_ana_lv_thresh_01

³⁵ IF imp_ana_lv_pulse_01 =0.5 THEN imp_ana_lv_thresh_01_05 = imp_ana_lv_thresh_01

³⁶ IF imp_ana_lv_pulse_01 = 0.4 THEN imp_ana_lv_pns_amp_01_04 = imp_ana_lv_pns_amp_01

³⁷ IF imp_ana_lv_pulse_01 = 0.5 THEN imp_ana_lv_pns_amp_01_05 = imp_ana_lv_pns_amp_01

Implantation Analyzer Data / LV /12 Pacing Vectors / Not-measured

Data file, identifier_patient_display_id_full	Descriptive	Variable name	Variable label, NEW prefix added to all labels "Implantation analyzer data, [specification ... to ...]: "	Variable level	Nominal values
implantation_analyzer_data	No	imp_ana_lv_imp_01_no	-	nominal	Above range Below range Not done
data_SAR	Yes	imp_ana_lv_imp_01_no_SAR ³⁸	Implantation analyzer data, LV1 tip to LV2 ring: Pacing impedance	nominal	Out of range Measured
implantation_analyzer_data	Yes	imp_ana_lv_thresh_01_no	no capture with maximum output possible	nominal	True / False
implantation_analyzer_data	Yes	imp_ana_lv_pns_01	Phrenic nerve stimulation detected	nominal	Yes / No

The above analyzes are performed for all 12 vector permutations, respectively.

³⁸ IF imp_ana_lv_imp_01_no = Above range OR Below range THEN imp_ana_lv_imp_01_no_SAR = Out of range
ELSE IF imp_ana_lv_imp_01 ≠ missing THEN imp_ana_lv_imp_01_no_SAR = Measured

Implantation Device Data / RA

Data file, identifier patient_display_id_full	Descriptive	Variable name	Variable label, NEW prefix added to all labels "Implantation device data, RA:"	Variable level	Nominal values
implantation_device_data	Yes	imp_ra_amp	Sensing amplitude [mV]	metric	n.a.
implantation_device_data	Yes	imp_ra_imp	Pacing impedance [Ω]	scale	n.a.
implantation_device_data	Yes	imp_ra_thresh	Pacing threshold [V] at Pulse width 0.4 ms	scale	n.a.

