Multipole_pacing	Yes	mpp_lv_first_reason	Main reason for vector choice	nominal	According to clinical routine Lowest available threshold To prevent phrenic nerve stimulation Best anatomical position Best available threshold [...] According to recommended [...] Other
Multipole_pacing	Reporting for each pt. if the above variable = other	mpp_lv_first_reason_co	[NEW] Multipole pacing data: Comments related to programmed first vector	text	...

Data file, identifier patient_ display_id_full	Descriptive	Variable name	Variable label, NEW prefix added to all labels "Multipole pacing data, second LV pacing vector: "	Variable level	Nominal values
Multipole_pacing	Yes	mpp_lv_sec_pvect	Programmed second LV pacing vector	nominal	[...]
Multipole_pacing	Yes	mpp_lv_sec_reason	Main reason for vector choice	nominal	According to clinical routine Lowest available threshold To prevent phrenic nerve stimulation Best anatomical position Best available threshold [...] According to recommended [...] Other
Multipole_pacing	Reporting for each pt. if the above variable = other	mpp_lv_sec_reason_co	[NEW] Multipole pacing data: Comments related to programmed second vector	text	...
data_SAR	Yes	mpp_lv_first_sec_pvect_SAR ⁵⁶	Programmed first and second LV pacing vector	nominal	#

A large number of combinations of vector pairs for MPP is possible. Only the most frequent combinations will be reported.
Combinations of two vectors for MPP in which only the designation as "first" and "second" are exchanged will be reported as one.

⁵⁶ mpp_lv_first_sec_pvect_SAR = combination of mpp_lv_first_pvect and mpp_lv_sec_pvect per patient

Multipole Pacing / LV / 12 Pacing Vectors

Data file, identifier_patient_display_id_full	Descriptive	Variable name	Variable label, NEW prefix added to all labels "Multipole pacing data, [specification ... to ...]: "	Variable level	Nominal values
Multipole_pacing	Yes	mpp_lv_imp_01	Pacing impedance [Ω]	scale	n.a.
Multipole_pacing	No	mpp_lv_thresh_01	Pacing threshold [V]	scale	n.a.
Multipole_pacing	No	mpp_lv_pulse_01	at Pulse width [ms]	scale	n.a.
data_SAR	Yes	mpp_lv_thresh_01_04 ⁵⁷	Pacing threshold [V] at 0.4 ms	scale	n.a.
data_SAR	Yes	mpp_lv_thresh_01_15 ⁵⁸	Pacing threshold [V] at 1.0 or 1.5 ms	scale	n.a.
Multipole_pacing	Yes	mpp_lv_pns_amp_01	Phrenic nerve stimulation at pacing amplitude [V]	scale	n.a.

A pacing threshold must always consist of amplitude and duration (pulse width). It is not reasonable to report one without the other.

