Here, the CIP does not suggest a specific pulse duration.

In the SAP version 1.0 it has been defined that it will be tested during blind review whether a meaningful number of measurements were performed with another pulse duration than 0.4 ms.

This test showed that most threshold measurements were done with 0.4 ms, but a number were done with 1.0 or 1.5 ms. These will be reported additionally to those at 0.4 ms, because long pulse durations indicate that the threshold was high at shorter pulse durations.

Thresholds of 1.0 and 1.5 ms duration will be summarized because the thresholds at these durations are similar.

The above analyses are performed for the following 12 vector permutations, respectively:

- 01 LV1 tip to LV2 ring
- 02 LV1 tip to LV4 ring
- 03 LV1 tip to RV coil
- 04 LV1 tip to ICD
- 05 LV2 ring to LV1 tip
- 06 LV2 ring to LV4 ring
- 07 LV2 ring to RV coil
- 08 LV3 ring to LV2 ring
- 09 LV3 ring to LV4 ring
- 10 LV3 ring to RV coil
- 11 LV4 ring to LV2 ring
- 12 LV4 ring to RV coil

⁵⁷ IF mpp_lv_pulse_01 = 0.4, THEN mpp_lv_thresh_01_04 = mpp_lv_thresh_01

⁵⁸ IF mpp_lv_pulse_01 = 1.0 OR 1.5, THEN mpp_lv_thresh_01_15 = mpp_lv_thresh_01

Multipole Pacing / LV / 12 Pacing Vectors / Not-measured

Data file, identifier <small>patient_</small> <small>display_id_full</small>	Descriptive	Variable name	Variable label, NEW prefix added to all labels	Variable level	Nominal values
Multipole_pacing	No	mpp_lv_imp_01_no	-	nominal	Out of range > 3000 out of range < 200 Not done
data_SAR	Yes	mpp_lv_imp_01_no SAR ⁵⁹	Multipole pacing data, LV1 tip to LV2 ring: Pacing impedance	nominal	Out of range Measured
Multipole_pacing	No	mpp_lv_thresh_01_no	-	nominal	True / False
data_SAR	Yes	mpp_lv_thresh_01_no_SAR ⁶⁰	Multipole pacing data, LV1 tip to LV2 ring: Pacing threshold	nominal	No capture with 7.5 V possible Measured
Multipole_pacing	Yes	mpp_lv_pns_01	Phrenic nerve stimulation detected	nominal	Yes / No

The above analyzes are performed for all 12 vector permutations, respectively.

Multipole Pacing / LV / Programmed Delay

Data file, identifier <small>patient_</small> <small>display_id_full</small>	Descriptive	Variable name	Variable label, NEW prefix added to all "Multipole pacing data: "	Variable level	Nominal values
Multipole_pacing	Yes	mpp_lvlv_delay_reason	NEW: Main reason for choice of delay LV-LV	nominal	According to recommended [...] Standard setting used Best hemodynamic response [...] Other

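### SAP 12.2 summarises the phrenic nerve stimulation amplitude of the 12 LV vectors without regard to pulse width, although it splits the capture threshold beside it, and SAP 10.2 splits the same quantity, by width

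*SAP*

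**What the plan says.** SAP 12.2, table on the 12 pacing vectors in the MultiPole Pacing data, plans these descriptive variables for each vector:

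- Capture threshold: the raw field is Descriptive = No. Two derived fields replace it, by footnote 57, "IF mpp_lv_pulse_01 = 0.4, THEN mpp_lv_thresh_01_04 = mpp_lv_thresh_01", and footnote 58, "IF mpp_lv_pulse_01 = 1.0 OR 1.5, THEN mpp_lv_thresh_01_15 = mpp_lv_thresh_01".
- PNS amplitude: the raw field `mpp_lv_pns_amp_01`, labelled "Phrenic nerve stimulation at pacing amplitude [V" (in volts), is Descriptive = Yes. It has no width in its label, no filter and no derived version.

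The text under that table states the principle: "A pacing threshold must always consist of amplitude and duration (pulse width). It is not reasonable to report one without the other". It then gives the result of the blind review: "This test showed that most threshold measurements were done with 0.4 ms, but a number were done with 1.0 or 1.5 ms". It justifies one pooling only: "Thresholds of 1.0 and 1.5 ms duration will be summarized because the thresholds at these durations are similar".

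SAP 10.2 treats the corresponding PNS item of the implant analyzer data differently. The raw amplitude is Descriptive = No, and PNS thresholds are derived separately at 0.4 and 0.5 ms (footnotes 36 and 37). Footnote 36 reads "IF imp_ana_lv_pulse_01 = 0.4 THEN imp_ana_lv_pns_amp_01_04 = imp_ana_lv_pns_amp_01".

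Mixed widths are possible because CIP 8.5.11 leaves the LV pulse width free, and SAP 12.2 notes that the CIP suggests no particular width for this test.

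**The concern.** A stimulation threshold in volts depends on the pulse width at which it is measured: a longer pulse needs less voltage. A PNS amplitude found at 1.0 or 1.5 ms is therefore not on the same scale as one found at 0.4 ms. The SAP accepts this for capture in the same table, and for PNS itself in 10.2, but 12.2 drops the distinction for PNS and gives no reason. It looks like an omission made when the capture split was added after blind review.

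What is at stake is how one descriptive table reads. CIP 8.5.6 requires all 12 vectors to be measured for both capture and PNS thresholds, and PNS is among the MultiPole Pacing risks discussed in CIP 6.2.3. The report would show, vector by vector, capture thresholds specific to a width next to a PNS amplitude that is not. A reader would naturally compare the two.

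**Working it through.** The plan gives no figure on this point, so there is none to reproduce. The check has two parts.

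**1. Handling of pulse width, side by side**

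| Quantity | Place | Raw field reported? | Split by width |
|---|---|---|---|
| LV capture, analyzer | SAP 10.2, fn 34-35 | No | 0.4 / 0.5 ms |
| LV PNS, analyzer | SAP 10.2, fn 36-37 | No | 0.4 / 0.5 ms |
| LV capture, MultiPole Pacing | SAP 12.2, fn 57-58 | No | 0.4 / 1.0 or 1.5 ms |
| LV PNS, MultiPole Pacing | SAP 12.2 | Yes | none |

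Three of the four are split; the fourth is not. Because it has no filter, the fourth would also take in any other width, which the capture derivations leave out.

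**2. How much the mixing could matter (illustration)**

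Inputs from the documents: the widths 0.4, 0.5, 1.0 and 1.5 ms. Everything else is assumed:

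- Strength-duration curve V(t) proportional to 1 + c/t, with c from 0.2 to 0.8 ms.
- Share s of PNS values obtained at long pulses from 5% to 30%, divided equally between 1.0 and 1.5 ms.
- The same underlying PNS threshold whichever width was used.
- Each PNS test made at the vector's recorded pulse width.

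Threshold relative to 0.4 ms, r(t) = (1 + c/t) / (1 + c/0.4):

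- c = 0.2: r(1.0) = 1.2/1.5 = 0.800; r(1.5) = 1.133/1.5 = 0.756
- c = 0.4: r(1.0) = 1.4/2.0 = 0.700; r(1.5) = 1.267/2.0 = 0.633
- c = 0.8: r(1.0) = 1.8/3.0 = 0.600; r(1.5) = 1.533/3.0 = 0.511

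Ratio of the higher to the lower threshold for each pair of widths, over c = 0.2-0.8:

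- 0.4 versus 1.0 ms: 1.25 to 1.67
- 0.4 versus 1.5 ms: 1.32 to 1.96
- 0.4 versus 0.5 ms: 1.07 to 1.15 (kept apart for PNS in SAP 10.2)
- 1.0 versus 1.5 ms: 1.06 to 1.17 (joined on purpose for capture in SAP 12.2)

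Under this curve, then, the SAP separates the smaller difference for PNS in 10.2 and lets the larger one be pooled in 12.2.

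Pooled mean relative to the 0.4 ms mean, m = (1 - s) + s × [r(1.0) + r(1.5)]/2:

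| c (ms) | s = 5% | s = 10% | s = 20% | s = 30% |
|---|---|---|---|---|
| 0.2 | 0.989 | 0.978 | 0.956 | 0.933 |
| 0.4 | 0.983 | 0.967 | 0.933 | 0.900 |
| 0.8 | 0.978 | 0.956 | 0.911 | 0.867 |

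The pooled mean is 1.1% (0.989) to 13.3% (0.867) below the 0.4 ms mean.

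**The case against.** The strongest reply is that the principle in SAP 12.2 is worded for a pacing threshold, and that the blind-review finding speaks of threshold measurements without naming PNS. No passage states the widths at which the PNS tests were done. That stands as a limit: using the vector's pulse-width field for PNS is an assumption. It is, however, the assumption SAP 10.2 makes in footnotes 36 and 37, and those footnotes, more than the worded principle, show that the SAP regards PNS as dependent on width.

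It can also be said that most threshold measurements were at 0.4 ms and that SAP 5.1 reports the median and quartiles as well as the mean, so a minority of long pulses may move the median little. This stands too.

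Several stronger readings are tempting, but the documents do not support them:

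- *That the PNS summary is meaningless.* With most tests at 0.4 ms it is a contaminated summary, and the width is recorded, so the split can be recovered.
- *That some vectors will look worse than others because of the test setting.* This needs a mix of widths that differs between vectors, and the SAP gives no breakdown by vector.
- *That the error is 20-49%.* That is the shift of a single measurement under the assumed curve (1 - 0.800 to 1 - 0.511), not the error of the planned summary.
- *That the table yields a wrong safety margin or affects vector choice.* No PNS-minus-capture margin is planned, and CIP 8.5.6 has vectors chosen patient by patient at programming, before any summary exists.

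Finally, SAP 12.6 states no hypotheses, and the CIP treats PNS as temporary and largely avoidable (CIP 6.2.3 and 6.4). This limits the weight of the point but does not explain the inconsistency.

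**Conclusion.** The point holds as an inconsistency in one descriptive variable. Followed as written, SAP 12.2 produces a PNS summary that can mix pulse widths which the SAP itself does not pool for capture in the same table, and which is not on the scale of the capture thresholds beside it. This depends on the PNS tests having used the vector's recorded width.

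A downward bias of the mean is possible, but neither its direction nor its size is certain. The figure of about 1-13% rests on the assumed 5-30% long-pulse share, the assumed curve (c = 0.2-0.8 ms) and equal underlying PNS thresholds in short-pulse and long-pulse tests. The SAP takes a long pulse as a sign of a high threshold at shorter widths. If PNS thresholds were also higher in those tests, the shift could be smaller. Whether the mix differs between vectors is not documented.

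No primary or secondary endpoint, error rate or sample size is affected. The correction is worth making because it is simple and the SAP already contains the pattern for it.

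**What to change.** In SAP 12.2, for all 12 vectors (xx = 01 to 12):

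- Set `mpp_lv_pns_amp_xx` to Descriptive = No.
- Derive `mpp_lv_pns_amp_xx_04`: IF `mpp_lv_pulse_xx` = 0.4 THEN `mpp_lv_pns_amp_xx_04` = `mpp_lv_pns_amp_xx`.
- Derive `mpp_lv_pns_amp_xx_15`: IF `mpp_lv_pulse_xx` = 1.0 OR 1.5 THEN `mpp_lv_pns_amp_xx_15` = `mpp_lv_pns_amp_xx`.
- Put the pulse width in both labels, and list individual values where the long-pulse cell is very small.
- State that the vector's recorded pulse width is taken to apply to its PNS test, after checking this against the CRF.

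This mirrors footnotes 57 and 58. It costs two derived variables per vector from fields already collected.

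The downside is small cells. The CIP plans 53 CRT-D patients and expects PNS in one or more vectors in about 40% of cases: 53 × 0.40 ≈ 21 patients over all 12 vectors. If amplitudes are recorded only where PNS occurred (assumed), some long-pulse cells may hold very few values, hence the listing. A per-patient difference between PNS and capture threshold at the same width would be an optional extra and is not part of the correction.

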12.3. Treatment of Missing and Spurious Data

See general definitions in chapter 5.4.

12.4. Exclusion of Particular Information

See general definitions in chapter 5.5.

12.5. Descriptive Analyses

See general definitions in chapter 5.1.

12.6. Hypotheses & Statistical Tests

There are no pre-defined statistical hypotheses.

13. Three-month Follow-up Data: Ilivia

13.1. Analysis set

All analyses are performed for the Ilivia analysis set⁶⁶.

13.2. Variables

3mFU General data

Data file, identifier patient_display_id_full	Descriptive	Variable name	Variable label, NEW prefix added to all labels "3mFU data: "	Variable level	Nominal values
fu_3_month_general_data	No	fu3_visdate	Date of 3-month follow-up	date	n.a.
fu_3_month_general_data	Yes	fu3_not_done	visit not performed	nominal	True / False
fu_3_month_general_data	Yes	fu3_interim	Did another follow-up occur since Pre-hospital discharge	nominal	Yes / No
fu_3_month_general_data	Yes	fu3_interim_reason	NEW: Reason for another FU	nominal	Home Monitoring alert Medical symptoms Other

The following variables are analyzed as defined for the Ilivia analysis set, as described in chapter 11.2.

3mFU Device Data / RA

3mFU Device Data / RA / Not-measured

3mFU Device Data / RV

3mFU Device Data / RV / Not-measured

3mFU Device Data / LV / Programmed Pacing Vectors

3mFU Device Data / LV / Programmed Pacing Vectors / Not-measured

3mFU Device Data / LV / Vector Change

3mFU Device Data / LV / Programmed Delay

3mFU Device Data / CRT / Atrial burden

3mFU Device Data / LV / Programmed Sensing Vector

Data file, identifier patient_display_id_full	Descriptive	Variable name	Variable label, NEW prefix added to all labels "3m FU data: "	Variable level	Nominal values
fu_3_month_device_data	Yes	fu3_lv_svect	Permanent programmed sensing vector	nominal	[...]
fu_3_month_device_data	Yes	fu3_lv_amp	Sensing amplitude [mV]	scale	n.a.

⁶⁶ analysis_set_Ilivia_SAR = Yes

3mFU Device Data / LV / Programmed Sensing Vector / Not-measured

Data file, identifier patient_display_id_full	Descriptive	Variable name	Variable label	Variable level	Nominal values
fu_3_month_device_data	No	fu3_lv_amp_no	-	nominal	No intrinsic rhythm Amplitude visible but too low to measure During intrinsic rhythm no R-wave visible Not done
data_SAR	Yes	fu3_lv_amp_no_SAR ⁶⁷	Implantation device data, any LV pacing vector: Sensing amplitude	nominal	Amplitude visible but too low to measure During intrinsic rhythm no R-wave visible Measured

3mFU Device Data / RA /System performance

Data file, identifier patient_display_id_full	Descriptive	Variable name	Variable label, NEW prefix added to all labels "3mFU data: "	Variable level	Nominal values
fu_3_month_device_data	No	fu3_perf_ra_sens	Adequate RA sensing	nominal	Yes / No
fu_3_month_device_data	Yes	fu3_perf_ra_sens_reason	Reason for inadequate RA sensing	nominal	Oversensing Undersensing Other
fu_3_month_device_data	Yes	fu3_perf_ra_pac	Adequate RA pacing	nominal	Yes / No
fu_3_month_device_data	Yes	fu3_perf_ra_pac_reason	Reason for inadequate RA pacing	nominal	Non-capture No output Other
fu_3_month_device_data	Yes	fu3_perf_ra_pac_nocap	NEW: Reason for non-capture RA		medical [...] technical

3mFU Device Data / RV/ System performance

Data file, identifier patient_display_id_full	Descriptive	Variable name	Variable label, NEW prefix added to all labels "3mFU data: "	Variable level	Nominal values
fu_3_month_device_data	No	fu3_perf_rv_sens	Adequate RV sensing	nominal	Yes / No
fu_3_month_device_data	Yes	fu3_perf_rv_sens_reason	Reason for inadequate RV sensing	nominal	Oversensing Undersensing Other
fu_3_month_device_data	Yes	fu3_perf_rv_pac	Adequate RV pacing	nominal	Yes / No
fu_3_month_device_data	Yes	fu3_perf_rv_pac_reason	Reason for inadequate RV pacing	nominal	Non-capture No output Other
fu_3_month_device_data	Yes	fu3_perf_rv_pac_nocap	NEW: Reason for non-capture RV		medical [...] technical

⁶⁷ IF fu3_lv_amp_no = Amplitude visible ... OR
fu3_lv_amp_no = During intrinsic rhythm... THEN fu3_lv_amp_no_SAR = fu3_lv_amp_no
ELSE IF fu3_lv_amp ≠ missing THEN fu3_lv_amp_no_SAR = Measured

3mFU Device Data / LV /System performance

Data file, identifier patient_display_id_full	Descriptive	Variable name	Variable label, NEW prefix added to all labels "3mFU data: "	Variable level	Nominal values
fu_3_month_ device_data	No	fu3_perf_lv_sens	Adequate LV sensing	nominal	Yes / No
fu_3_month_ device_data	Yes	fu3_perf_lv_sens_ reason	Reason for inadequate LV sensing	nominal	Oversensing Undersensing Other
fu_3_month_ device_data	Yes	fu3_perf_lv_pac	Adequate LV pacing	nominal	Yes / No
fu_3_month_ device_data	Yes	fu3_perf_lv_pac_ reason	Reason for inadequate LV pacing	nominal	Non-capture No output Other
fu_3_month_ device_data	Yes	fu3_perf_lv_pac_ nocap	NEW: Reason for non- capture LV		medical [...] technical

13.3. Treatment of Missing and Spurious Data

See general definitions in chapter 5.4.

13.4. Exclusion of Particular Information

See general definitions in chapter 5.5.

13.5. Descriptive Analyses

See general definitions in chapter 5.1.

13.6. Hypotheses & Statistical Tests

There are no pre-defined statistical hypotheses.

14. Six-month Follow-up Data: Ilivia

14.1. Analysis set

All analyses are performed for the Ilivia analysis set⁶⁸.

14.2. Variables

6mFU / General data

Data file, identifier patient_display_id_full	Descriptive	Variable name	Variable label, NEW prefix added to all labels "6mFU data: "	Variable level	Nominal values
fu_6_month_general_data	No	fu6_visdate	Date of 6-month follow-up	date	n.a.
fu_6_month_general_data	Yes	fu6_not_done	visit not performed	nominal	True / False
fu_6_month_general_data	Yes	fu6_interim	Did another follow-up occur since 3-month Follow-up	nominal	Yes / No
fu_6_month_general_data	Yes	fu6_interim_reason	NEW: Reason for another FU	nominal	Home Monitoring alert Medical symptoms Other

6mFU / General Data / Heart Failure

Data file, identifier patient_display_id_full	Descriptive	Variable name	Variable label, NEW prefix added to all labels "6mFU data: "	Variable level	Nominal values
fu_6_month_general_data	No	fu6_hf	Heart failure	nominal	Yes / No
fu_6_month_general_data	Yes	fu6_nyha	Heart failure status	nominal	NYHA I NYHA II NYHA III NYHA IV
fu_6_month_general_data	Yes	fu6_responder	Responder to CRT-D therapy	nominal	Yes / No

⁶⁸ analysis_set_Ilivia_SAR = Yes

The following variables are analyzed as defined for the Ilivia analysis set, as described in chapter 13.2.

6mFU Device Data / RA

6mFU Device Data / RA / Not-measured

6mFU Device Data / RV

6mFU Device Data / RV / Not-measured

6mFU Device Data / LV / Programmed Sensing Vector

6mFU Device Data / LV / Programmed Sensing Vector / Not-measured

6mFU Device Data / LV / Programmed Pacing Vectors

6mFU Device Data / LV / Programmed Pacing Vectors / Not-measured

6mFU Device Data / LV / Vector Change

6mFU Device Data / LV / Programmed Delay

6mFU Device Data / CRT / Atrial burden

14.3. Treatment of Missing and Spurious Data

See general definitions in chapter 5.4.

14.4. Exclusion of Particular Information

See general definitions in chapter 5.5.

14.5. Descriptive Analyses

See general definitions in chapter 5.1.

14.6. Hypotheses & Statistical Tests

There are no pre-defined statistical hypotheses.

15. MRI Data: Ilivia

15.1. Analysis set

All analyses are performed for the Ilivia analysis set⁶⁹.

3mFU General Data / MRI

Data file, identifier patient_display_id_full	Descriptive	Variable name	Variable label, NEW prefix added to all labels "3mFU data: "	Variable level	Nominal values
fu_3_month_general_data	Yes	fu3_mri	Routine MRI scan performed since previous follow-up	nominal	Yes / No
fu_3_month_general_data	Yes	fu3_mri_autodetect	MRI AutoDetect feature used or attempted to be used	nominal	Yes / No

6mFU General Data / MRI

Data file, identifier patient_display_id_full	Descriptive	Variable name	Variable label, NEW prefix added to all labels "6mFU data: "	Variable level	Nominal values
fu_6_month_general_data	Yes	fu6_mri	Routine MRI scan performed since previous follow-up	nominal	Yes / No
fu_6_month_general_data	Yes	fu6_mri_autodetect	MRI AutoDetect feature used or attempted to be used	nominal	Yes / No

MRI AutoDetect

Data file, list of MRI events, identifier record_ID	Report all events without any statistics	Variable name	Variable label	Variable level	Nominal values
mri_autodetect	Yes	patient_display_id_full	Patient Display ID	nominal	...
mri_autodetect	Yes	mri_visdate	(Planned) date of MRI scan	nominal	Yes / No
mri_autodetect	Yes	mri_successful	MRI AutoDetect could be successfully programmed	nominal	Yes / No
mri_autodetect	Yes	mri_test_mode	Was the "MRI Test Mode" used to test the effect of programming the patient to MRI mode?	nominal	Yes / No
mri_autodetect	Yes	mri_deactivation_hm	Was deactivation of MRI mode checked via Home Monitoring the day after the scan	nominal	Yes / No
mri_autodetect	Yes	mri_ae_dd	Were any Adverse Events/ Device deficiencies detected in regard to the MRI procedure or activation of MRI AutoDetect?	nominal	Yes / No

